8.2.4. Proportion of CDA and CR at each Visit

The proportion of patients who are able to achieve CDA and the proportion of patients who are able to achieve CR will be summarized by maximum dose level and overall by CDA and CR status for each visit by using frequencies and percentages, respectively. This is a cross sectional analysis and differs from the cumulative assessment of efficacy described above. In addition, two-sided 80% and 95% CIs of the response rate will be provided for each maximum dose level and overall using the Exact (Clopper-Pearson) method.

The proportion of patients who are able to achieve CDA and/or CR without the need for doses of prednis(ol)one of greater than 0.5 mg/kg (CS doses from Day 1 to the day before the date of the visit) will also be summarized by maximum dose level and overall for each visit. Two-sided 80% and 95% CIs will be provided by using the Exact (Clopper-Pearson) method.

The disease status at each visit, and the CS dose on the day before the achievement date will be listed.

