Source Data: Listing 16.2.4.1.5

<DIRECTORY PATH>PROGRAM NAME Executed: DDMMYYYY hh:mm

Prog Note: For all efficacy and safety by visit summaries, add "unscheduled" visit after other visits if such data exist in the database.

Repeat the above table for the other populations

Table 14.2.2.4.1.2

Proportion of Patients who Achieved Control of Disease Activity (CDA) at Visit
mITT Population

Table 14.2.2.4.1.3

Proportion of Patients who Achieved Control of Disease Activity (CDA) at Visit
Per Protocol Population

Table 14.2.2.4.2.1

Proportion of Patients who Achieved Control of Disease Activity (CDA) without Prednis(ol)one >0.5 mg/kg at Visit
 ITT Population

Visit	400 mg (N=xx)	500 mg (N=xx)	600 mg (N=xx)	Total (N=xx)
WEEK3 D15				
n (%)	xx (xx.x)	xx (xx.x)	xx (xx.x)	xx (xx.x)
80% CONFIDENCE INTERVAL	(xx.x, xx.x)	(xx.x, xx.x)	(xx.x, xx.x)	(xx.x, xx.x)
95% CONFIDENCE INTERVAL	(xx.x, xx.x)	(xx.x, xx.x)	(xx.x, xx.x)	(xx.x, xx.x)
WEEK5 D29				
n (%)	xx (xx.x)	xx (xx.x)	xx (xx.x)	xx (xx.x)
80% CONFIDENCE INTERVAL	(xx.x, xx.x)	(xx.x, xx.x)	(xx.x, xx.x)	(xx.x, xx.x)
95% CONFIDENCE INTERVAL	(xx.x, xx.x)	(xx.x, xx.x)	(xx.x, xx.x)	(xx.x, xx.x)
...				
WEEK25 D169				
n (%)	xx (xx.x)	xx (xx.x)	xx (xx.x)	xx (xx.x)
80% CONFIDENCE INTERVAL	(xx.x, xx.x)	(xx.x, xx.x)	(xx.x, xx.x)	(xx.x, xx.x)
95% CONFIDENCE INTERVAL	(xx.x, xx.x)	(xx.x, xx.x)	(xx.x, xx.x)	(xx.x, xx.x)

Note: Patients are classified into different dose levels according to the maximum dose they received during the 12 week treatment period.
 Control of disease activity (CDA) is defined as the time at which new lesions cease to form and established lesions begin to heal.
 Patients who achieved CDA at a specific visit and had no occurrence of daily prednis(ol)one >0.5 mg/kg before each visit date during the study treatment will be counted as responders.
 Two-sided 80% and 95% confidence intervals are calculated using the Exact (Clopper-Pearson) method.
 Percentages are based on the number of patients in the respective dose levels in the Analysis Population.

Source Data: Listing 16.2.4.1.5

<DIRECTORY PATH>PROGRAM NAME Executed: DDMMYYYYY hh:mm

Prog Note: For all efficacy and safety by visit summaries, add "unscheduled" visit after other visits if such data exist in the database.

Repeat above table for other populations.

Table 14.2.2.4.2.2

Proportion of Patients who Achieved Control of Disease Activity (CDA) without Prednis(ol)one >0.5 mg/kg at Visit
mITT Population

Table 14.2.2.4.2.3

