 Complete response (CR) is defined as the absence of new or established lesions while the patient is receiving minimal or no non-PRN 1008 immunotherapy.
 Two-sided 80% and 95% confidence intervals are calculated using the Exact (Clopper-Pearson) method.
 Percentages are based on the number of patients in the respective dose levels in the Analysis Population.

Source Data: Listing 16.2.4.1.5

<DIRECTORY PATH>PROGRAM NAME Executed: DDMMYYYY hh:mm

Prog Note: For all efficacy and safety by visit summaries, add "unscheduled" visit after other visits if such data exist in the database.

Repeat for the following populations.

Table 14.2.2.5.1.2

Proportion of Patients who Achieved Complete Response (CR) at Visit
mITT Population

Table 14.2.2.5.1.3

Proportion of Patients who Achieved Complete Response (CR) at Visit
Per Protocol Population

Table 14.2.2.5.2.1

Proportion of Patients who Achieved Complete Response (CR) without Prednis(ol)one >0.5 mg/kg at Visit
 ITT Population

Visit	400 mg (N=xx)	500 mg (N=xx)	600 mg (N=xx)	Total (N=xx)
WEEK3 D15				
n (%)	xx (xx.x)	xx (xx.x)	xx (xx.x)	xx (xx.x)
80% CONFIDENCE INTERVAL	(xx.x, xx.x)	(xx.x, xx.x)	(xx.x, xx.x)	(xx.x, xx.x)
95% CONFIDENCE INTERVAL	(xx.x, xx.x)	(xx.x, xx.x)	(xx.x, xx.x)	(xx.x, xx.x)
WEEK5 D29				
n (%)	xx (xx.x)	xx (xx.x)	xx (xx.x)	xx (xx.x)
80% CONFIDENCE INTERVAL	(xx.x, xx.x)	(xx.x, xx.x)	(xx.x, xx.x)	(xx.x, xx.x)
95% CONFIDENCE INTERVAL	(xx.x, xx.x)	(xx.x, xx.x)	(xx.x, xx.x)	(xx.x, xx.x)
...				
WEEK25 D169				
n (%)	xx (xx.x)	xx (xx.x)	xx (xx.x)	xx (xx.x)
80% CONFIDENCE INTERVAL	(xx.x, xx.x)	(xx.x, xx.x)	(xx.x, xx.x)	(xx.x, xx.x)
95% CONFIDENCE INTERVAL	(xx.x, xx.x)	(xx.x, xx.x)	(xx.x, xx.x)	(xx.x, xx.x)

Note: Patients are classified into different dose levels according to the maximum dose they received during the 12 week treatment period.

Complete response (CR) is defined as the absence of new or established lesions while the patient is receiving minimal or no non-PRN 1008 immunotherapy.

Patients who achieved CR at a specific visit and had no occurrence of daily prednis(ol)one >0.5 mg/kg on or before the first CR date during the study treatment will be counted as responders.

Two-sided 80% and 95% confidence intervals are calculated using the Exact (Clopper-Pearson) method.

Percentages are based on the number of patients in the respective dose levels in the Analysis Population.

Only Systemetic Corticosteroids are considered for this table.

Source Data: Listing 16.2.4.1.5

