<DIRECTORY PATH>PROGRAM NAME Executed: DMMMMYYYY hh:mm

Prog Note: For all efficacy and safety by visit summaries, add "unscheduled" visit after other visits if such data exist in the database.

Repeat for the following populations

Table 14.2.2.5.2.2

Proportion of Patients who Achieved Complete Response (CR) without Prednis(ol)one >0.5 mg/kg at Visit
mITT Population

Table 14.2.2.5.2.3

Proportion of Patients who Achieved Complete Response (CR) without Prednis(ol)one >0.5 mg/kg at Visit
Per Protocol Population

Table 14.2.2.5.3.1
 Proportion of Patients who Achieved Complete Response (CR) with Prednis(ol)one >0.5 mg/kg at Visit
 ITT Population

Visit	400 mg (N=xx)	500 mg (N=xx)	600 mg (N=xx)	Total (N=xx)
WEEK3 D15				
n (%)	xx (xx.x)	xx (xx.x)	xx (xx.x)	xx (xx.x)
80% CONFIDENCE INTERVAL	(xx.x, xx.x)	(xx.x, xx.x)	(xx.x, xx.x)	(xx.x, xx.x)
95% CONFIDENCE INTERVAL	(xx.x, xx.x)	(xx.x, xx.x)	(xx.x, xx.x)	(xx.x, xx.x)
WEEK5 D29				
n (%)	xx (xx.x)	xx (xx.x)	xx (xx.x)	xx (xx.x)
80% CONFIDENCE INTERVAL	(xx.x, xx.x)	(xx.x, xx.x)	(xx.x, xx.x)	(xx.x, xx.x)
95% CONFIDENCE INTERVAL	(xx.x, xx.x)	(xx.x, xx.x)	(xx.x, xx.x)	(xx.x, xx.x)
...				
WEEK25 D169				
n (%)	xx (xx.x)	xx (xx.x)	xx (xx.x)	xx (xx.x)
80% CONFIDENCE INTERVAL	(xx.x, xx.x)	(xx.x, xx.x)	(xx.x, xx.x)	(xx.x, xx.x)
95% CONFIDENCE INTERVAL	(xx.x, xx.x)	(xx.x, xx.x)	(xx.x, xx.x)	(xx.x, xx.x)

Note: Patients are classified into different dose levels according to the maximum dose they received during the 12 week treatment period.
 Complete response (CR) is defined as the absence of new or established lesions while the patient is receiving minimal or no non-PRN 1008 immunotherapy.
 Patients who achieved CR at a specific visit and had daily prednis(ol)one >0.5 mg/kg on or before the first CR date during the study treatment will be counted as responders.
 Two-sided 80% and 95% confidence intervals are calculated using the Exact (Clopper-Pearson) method.
 Percentages are based on the number of patients in the respective dose levels in the Analysis Population.
 Only Systemetic Corticosteroids are considered for this table.
 Source Data: Listing 16.2.4.1.5

<DIRECTORY PATH>PROGRAM NAME Executed: DMMMMYYYY hh:mm
 Prog Note: For all efficacy and safety by visit summaries, add "unscheduled" visit after other visits if such data exist in the database.
 Repeat for the following populations

Table 14.2.2.5.3.2

Proportion of Patients who Achieved Complete Response (CR) with Prednis(ol)one >0.5 mg/kg at Visit

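### Part A SAP: the CR-at-visit shells check high-dose steroid only up to first CR, whereas section 8.2.4 checks it up to the day before each visit

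*SAP*

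**What the plan says.** Part A SAP section 8.2.4 sets out CDA and CR at each visit. It states the nature of the summary: "This is a cross sectional analysis and differs from the cumulative assessment of efficacy described above". For the version restricted to patients without prednis(ol)one above 0.5 mg/kg, the steroid window is "CS doses from Day 1 to the day before the date of the visit". The window therefore moves forward with the visit being tabulated.

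The Part A table shells implement this as follows.

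- Table 14.2.2.5.2.1 (CR *without*, at visit) counts "Patients who achieved CR at a specific visit and had no occurrence of daily prednis(ol)one >0.5 mg/kg on or before the first CR date".
- Table 14.2.2.5.3.1 (CR *with*, at visit) counts patients who "had daily prednis(ol)one >0.5 mg/kg on or before the first CR date during the study treatment will be counted as responders".
- Both shells are repeated for the mITT and per-protocol populations.
- Table 14.2.2.4.2.1 (CDA *without*, at visit) requires "no occurrence of daily prednis(ol)one >0.5 mg/kg before each visit date during the study treatment will be counted as responders".
- Listing 16.2.4.1.5, which the CR tables name as their source, flags high-dose steroid up to and including the visit concerned.

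**The concern.** One named secondary summary has two responder rules. In the CR shells the steroid check is fixed at first CR, whichever visit is being reported. High-dose steroid taken after a relapse is then invisible at every later visit, and a CR regained after that steroid is reported as CR on low-dose steroid or none.

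The window carries the whole distinction between the two tables. Part A SAP section 3.2.3 already limits CR to patients on no more than 10 mg/day of prednisolone equivalent, so the dose at the CR visit can hardly separate *with* from *without* in an adult. Only the look-back separates them, and that is the element in conflict. Two programmers, one working from section 8.2.4 and one from the shell, could produce different tables from the same data.

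**Working it through.** **1. The windows side by side, for a patient in CR at visit v**

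| Source | Steroid is checked |
|---|---|
| Part A SAP 8.2.4 | Day 1 to the day before v |
| Tables 14.2.2.5.2.x and 14.2.2.5.3.x (CR) | up to and including the first CR date, during study treatment |
| Table 14.2.2.4.2.1 (CDA *without*) | before v, during study treatment |
| Listing 16.2.4.1.5 (source) | up to and including v, during study treatment |

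The CR shells are the only ones not tied to v.

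**2. Direction of the difference.** First CR cannot fall after v. At any later CR visit the shell window is therefore contained in the 8.2.4 window, and the shell can only add patients to *without* and remove them from *with*. At the first CR visit the two rules differ only on whether the visit day itself is included.

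**3. Why the dose on the day does not separate the tables.** A dose of 10 mg exceeds 0.5 mg/kg only below 10 / 0.5 = 20 kg body weight. Protocol section 1.4.2.1 reports CR on up to 20 mg/day; even that exceeds 0.5 mg/kg only below 20 / 0.5 = 40 kg.

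**4. One hypothetical patient.** First CR on Day 57, more than 0.5 mg/kg on Days 70 to 99, CR recorded again on Days 141 and 169.

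| Visit | In CR | *Without* under 8.2.4 | *Without* under the CR shell |
|---|---|---|---|
| Week 9 (Day 57) | yes | yes | yes |
| Week 13 (Day 85) | no | no | no |
| Week 17 (Day 113) | no | no | no |
| Week 21 (Day 141) | yes | no | yes |
| Week 25 (Day 169) | yes | no | yes |

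The dates are chosen to exercise the rules. A slower taper would leave only the Week 25 visit in dispute.

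**5. Consequence across tables.** In this example the high-dose steroid starts while PRN1008 is still being given, since Part A dosing ends at Day 84 or 85. The CDA shell therefore excludes the patient from CDA *without* at Weeks 21 and 25, while the CR shell includes the same patient in CR *without*. A patient with no lesions has disease control, and Part B SAP section 3.4.7 says outright that CR implies CDA, so the two table sets would not reconcile.

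**6. Scale.** Part A SAP section 4.1 plans 25 patients. Its stated 80% precision is reproduced by 1.2816 × √(0.5 × 0.5 / 25) = 0.128, or ±13 points. One reclassified patient is 1/25 = 4 points. For example, 5/25 = 20% (exact 80% CI 10.1 to 34.0) becomes 6/25 = 24% (13.1 to 38.3). With 0 to 2 such patients, an assumed range, the shift is 0 to 2/25 = 0 to 8 points. In a dose-level column with fewer patients, each step is larger.

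**The case against.** The case against making much of this is substantial, and most of it stands.

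- *The route is narrow.* Rescue alone is not enough: the steroid must follow first CR, and CR must be recorded again. Under the Part A rescue criteria, 1.0 mg/kg with PRN1008 continued applies to severe disease with trough occupancy below 50% or not available, and protocol section 2.1 reports adequate occupancy in 20 of 21 patients. The failure-to-control criterion uses 0.5 mg/kg, which does not exceed the threshold. The taper table in protocol Appendix 7 needs eight weekly steps from 40 mg to 10 mg, so regaining CR within four weeks of rescue is implausible; Weeks 21 to 25 are the likely visits.
- *The body text is right and the listing shows the facts.* Section 8.2.4 and Listing 16.2.4.1.5 would let a careful programmer classify correctly. That lowers the risk but leaves the tables' own footnotes giving a different rule.
- *The CDA shell is not a clean model.* It limits the check to steroid during study treatment, words that 8.2.4 lacks. The tables run to Week 25, and Part A dosing ends around Week 13. If the phrase drops steroid taken off treatment, the CDA shell departs from 8.2.4 as well.

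A reader might also combine the protocol's interim figures (section 1.4.2.1: two patients needing high-dose steroid, four reaching CR) into an estimate of inflation. The documents do not support that. They report no overlap between the groups. The high-dose steroid was given during PRN1008 treatment, and the CRs were reported at Week 13 (three) and Week 21 (one). In any overlapping patient the steroid most likely came before first CR, which makes the patient *with* under both rules. The denominators do not match either: three CRs given as 25% imply 3 / 0.25 = 12 patients, not the 18 with efficacy data.

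**Conclusion.** The inconsistency is real, and it changes who is counted. The by-visit CR shells contradict section 8.2.4, differ from the parallel CDA *without* shell and do not match their own source listing. Away from the first CR visit, the error runs one way, towards more CR *without* high-dose steroid.

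Its size is unknown. The shift of 0 to 8 points assumes 0 to 2 affected patients among 25, and zero is a possible answer. The step from CR *without* to CDA *without* at the same visit fails only if the high-dose steroid fell within study treatment as the CDA shell uses that term.

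A reader might infer that the trial's main efficacy result is at risk. It is not. The primary CDA endpoint (8.1) and CR within 12 weeks (8.2.2, 8.2.3) have their own rules. The cumulative CR tables have their own footnotes, where stopping at first CR suits a count of patients who ever responded. Section 8.2.5 repeats the day-before-the-visit parenthesis for those summaries, but there the visit can be read as the one at which response was reached, so they are not counted as affected. What remains is a correction that should be made to secondary by-visit tables, which SAP section 13 added to the protocol's list.

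**What to change.** - In Tables 14.2.2.5.2.x, replace the footnote condition with: in CR at the visit, and no day from Day 1 to the day before that visit with a prednis(ol)one-equivalent dose above 0.5 mg/kg. In Tables 14.2.2.5.3.x, use the same window with at least one such day.
- Use the same window in the CDA by-visit shells. Either remove the limit to study treatment or define it for visits after Week 13, so that steroid taken off PRN1008 is handled the same way in every table.
- Correct the CDA *with* shell, Table 14.2.2.4.3.1. Its footnote carries the *without* condition, "no occurrence of daily prednis(ol)one >0.5 mg/kg before each visit date during the study treatment", and so describes the opposite group from its title.
- Part B SAP section 1 dates the last Part A completion to 20 June 2019. If the tables have already been produced, state which rule was programmed and rerun them if it was the shell's.

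The cost is footnote wording and one programming condition, with no new data. The CR *without* rate may fall slightly at later visits, with a matching rise in the *with* table.

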8.2.11. Subgroup Analysis

The rates of the primary endpoint will be calculated in selected subgroups:

1. Age (≥ 50 , < 50)
2. Gender
3. Total anti-desmoglein (dsg) antibody (≥ 100 , < 100 units) at baseline.
4. Pemphigus History Type: Newly diagnosed (≤ 6 months from screening) vs. relapsed (> 6 months)
5. Pemphigus Anti-DSG Profile at baseline: PV vs. PF vs. negative anti-dsg profile, where PV is defined as anti-dsg3 positive with anti-dsg1 negative or anti-dsg 3 positive with anti-dsg1 positive. PF=anti-dsg1 positive only vs. neither detectable).
6. Pemphigus Severity: Mild vs. moderate disease severity at baseline (PDAI total activity < 15 vs. ≥ 15). If screening PDAI is not available use Day 1.

9. Safety Analysis

Specific assessments to evaluate treatment safety include the following: the frequency and type of adverse events, clinical laboratory testing, brain MRI (baseline and Day 15 in a subset of patients), vital signs, and symptoms and/or signs of headache, nausea, vomiting or visual disturbances. All analyses of safety will be conducted using the Safety Analysis Population.

For by visit summaries, unscheduled visits, if they exist in the data, will be presented separately after other visits.

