PEMPHIGUS FOLLACEUS	xx (xx.x)	xx (xx.x)	xx (xx.x)	xx (xx.x)
EPIDERMOLYSIS BULLOSA AQUISITA	xx (xx.x)	xx (xx.x)	xx (xx.x)	xx (xx.x)
LINEAR IGA BULLOUS DERMATOSES	xx (xx.x)	xx (xx.x)	xx (xx.x)	xx (xx.x)
MUCOUS MEMBRANE PEMPFIGOID	xx (xx.x)	xx (xx.x)	xx (xx.x)	xx (xx.x)
OTHER	xx (xx.x)	xx (xx.x)	xx (xx.x)	xx (xx.x)
TIME FROM PEMPFIGUS VULGARIS CONFIRMED DATE TO SCREEN DATE (Months) [1]				
n	xx	xx	xx	xx
MEAN (SD)	xx.xxx (xx.xxxx)	xx.xxx (xx.xxxx)	xx.xxx (xx.xxxx)	xx.xxx (xx.xxxx)
MEDIAN	xx.xxx	xx.xxx	xx.xxx	xx.xxx
MIN, MAX	xx.xx, xx.xx	xx.xx, xx.xx	xx.xx, xx.xx	xx.xx, xx.xx
PEMPHIGUS HISTORY TYPE n (%) [2]				
NEWLY DIAGNOSED	xx (xx.x)	xx (xx.x)	xx (xx.x)	xx (xx.x)
RELAPSED	xx (xx.x)	xx (xx.x)	xx (xx.x)	xx (xx.x)
PEMPHIGUS ANTI-DSG PROFILE				
ANTI-DSG 3 POSITIVE (PV)	xx (xx.x)	xx (xx.x)	xx (xx.x)	xx (xx.x)
ANTI-DSG 1 POSITIVE AND ANTI-DSG 3 NEGATIVE (PF)	xx (xx.x)	xx (xx.x)	xx (xx.x)	xx (xx.x)
ANTI-DSG 1 NEGATIVE AND ANTI-DSG 3 NEGATIVE	xx (xx.x)	xx (xx.x)	xx (xx.x)	xx (xx.x)

Note: Patients are classified into different dose levels according to the maximum dose they received during the 12 week treatment period.

$$BMI = (\text{Baseline body weight in kilograms}) / (\text{Baseline height in meters})^2$$

[1] Time from pemphigus vulgaris confirmed date to screen date in months is defined as (Screening Date - Date of pemphigus vulgaris confirmed +1) / 30.4375

[2] Newly diagnosed is defined as subjects who were diagnosed at most 6 months prior to date of screening, otherwise the subject is relapsed.

Principia Biopharma Australia Pty Ltd.
PRN1008-005

Source Data: Listing 16.2.2.1
<DIRECTORY PATH>PROGRAM NAME Executed: DDMMYYYYY hh:mm

Table 14.1.2.1
Summary of Demographics and Baseline Characteristics
Safety Analysis Population

	400 mg (N=xx)	500 mg (N=xx)	600 mg (N=xx)	Total (N=xx)
PEMPHIGUS SEVERITY AT BASELINE				
MILD (PDAI ACTIVITY < 15)	xx (xx.x)	xx (xx.x)	xx (xx.x)	xx (xx.x)
MODERATE (PDAI ACTIVITY ≥ 15)	xx (xx.x)	xx (xx.x)	xx (xx.x)	xx (xx.x)
ANTI-DSG STATUS AT BASELINE n (%)				
ANTI-DSG 1 + and ANTI-DSG 3 -	xx (xx.x)	xx (xx.x)	xx (xx.x)	xx (xx.x)
ANTI-DSG 1 - and ANTI-DSG 3 +	xx (xx.x)	xx (xx.x)	xx (xx.x)	xx (xx.x)
ANTI-DSG 1 + and ANTI-DSG 3 +	xx (xx.x)	xx (xx.x)	xx (xx.x)	xx (xx.x)
ANTI-DSG 1 - and ANTI-DSG 3 -	xx (xx.x)	xx (xx.x)	xx (xx.x)	xx (xx.x)
TOTAL ANTI-DSG n (%)				
≥ 100	xx (xx.x)	xx (xx.x)	xx (xx.x)	xx (xx.x)
< 100	xx (xx.x)	xx (xx.x)	xx (xx.x)	xx (xx.x)
PDAI SKIN ACTIVITY > 0 n (%)	xx (xx.x)	xx (xx.x)	xx (xx.x)	xx (xx.x)

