Prog Note: Repeat Table 14.2.2.4.5 with the addition of page variable Pemphigus History Type (Newly Diagnosed vs Relapsed).

Add footnote: Newly diagnosed subjects are defined as diagnostic date being less than 6 months to Screening date, otherwise a subject is defined as relapsed.

Repeat for the following populations.

Table 14.2.10.4.2

Cumulative Incidents of Control of Disease Activity (CDA) without Predniso(lo)ne > 0.5mg/kg by Visit by
Pemphigus History Type
mITT Population

Table 14.2.10.4.3

Cumulative Incidents of Control of Disease Activity (CDA) without Predniso(lo)ne > 0.5mg/kg by Visit by
Pemphigus History Type
Per Protocol Population

Table 14.2.10.5.1

Cumulative Incidents of Control of Disease Activity (CDA) without Predniso(lo)ne > 0.5mg/kg by Visit by Pemphigus Anti-DSG Profile
ITT Population

Prog Note: Repeat Table 14.2.2.4.5 with the addition of page variable anti-dsg1 positive vs. anti-dsg1 positive anti-dag3 negative vs. neither positive.

Repeat for the following populations.

Table 14.2.10.5.2

Cumulative Incidents of Control of Disease Activity (CDA) without Predniso(lo)ne > 0.5mg/kg by Visit by Pemphigus Anti-DSG Profile
mITT Population

Table 14.2.10.5.3

Cumulative Incidents of Control of Disease Activity (CDA) without Predniso(lo)ne > 0.5mg/kg by Visit by Pemphigus Anti-DSG Profile
Per Protocol Population

Table 14.2.10.6.1

Cumulative Incidents of Control of Disease Activity (CDA) without Predniso(lo)ne > 0.5mg/kg by Visit by Pemphigus Anti-DSG Profile
ITT Population

Prog Note: Repeat Table 14.2.2.4.5 with the addition of page variable Pemphigus Severity: mild vs moderate. Add footnote: Mild Pemphigus subject is defined as screening PDAI < 15, otherwise moderate.

Repeat for the following populations.

Table 14.2.10.6.2

Cumulative Incidents of Control of Disease Activity (CDA) without Predniso(lo)ne > 0.5mg/kg by Visit by Pemphigus Anti-DSG Profile
mITT Population

Table 14.2.10.6.3

Cumulative Incidents of Control of Disease Activity (CDA) without Predniso(lo)ne > 0.5mg/kg by Visit by Pemphigus Anti-DSG Profile
Per Protocol Population

Table 14.3.1.1
 Overall Summary of Treatment-Emergent Adverse Events
 Safety Analysis Population

	400 mg (N=xx) n (%) [E]	500 mg (N=xx) n (%) [E]	600 mg (N=xx) n (%) [E]	Total (N=xx) n (%) [E]
ANY TREATMENT-EMERGENT ADVERSE EVENT	xx (xx.x) xx	xx (xx.x) xx	xx (xx.x) xx	xx (xx.x) xx
ANY SERIOUS TREATMENT-EMERGENT ADVERSE EVENT	xx (xx.x) xx	xx (xx.x) xx	xx (xx.x) xx	xx (xx.x) xx

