5.4.1.1 Subset Analyses

The robustness of the primary endpoint results will be explored by calculating the number and percent of patients meeting the primary efficacy endpoint overall (i.e. across all doses) within the following patient subsets:

- 1) Age (< 50 years, ≥ 50 years)
- 2) Gender
- 3) Total anti-desmoglein (DSG) antibody (≥ 100, < 100 units) at baseline.
- 4) Pemphigus History Type: Newly diagnosed (≤ 6 months from screening) vs. relapsed (> 6 months from screening)
- 5) Pemphigus anti-DSG Profile at baseline: Pemphigus Vulgaris (PV) vs. Pemphigus foliaceus (PF) vs. negative anti-DSG profile, defined as follows:
 - PV: anti-DSG3 positive with anti-DSG1 negative or anti-DSG3 positive with anti-DSG1 positive.
 - PF: anti-DSG1 positive only
 - Negative anti-DSG profile: neither detectable.
- 6) Pemphigus Severity: PDAI < 15 (mild-moderate) vs PDAI ≥ 15 (moderate-severe) at baseline If screening PDAI is not available use Week 1 Day 1 Pre-dose.

A sensitivity analysis using the Completer and PP populations will be provided for each subset analysis.

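### The Part A programming note for the anti-desmoglein profile tables names anti-DSG1 where the SAP names anti-DSG3, so patients positive only for anti-DSG3 have no page

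*SAP*

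**What the plan says.** Part A SAP section 8.2.11 introduces six subgroup splits with the sentence "The rates of the primary endpoint will be calculated in selected subgroups". Item 5 is the anti-desmoglein profile at baseline. There, "PV is defined as anti-dsg3 positive with anti-dsg1 negative or anti-dsg 3 positive with anti-dsg1 positive", and the other two groups are given as "PF=anti-dsg1 positive only vs. neither detectable".

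The baseline shell in the same set, Table 14.1.2.1, has a block for the same profile. Its first row is "ANTI-DSG 3 POSITIVE (PV" and its second is "ANTI-DSG 1 POSITIVE AND ANTI-DSG 3 NEGATIVE (PF" (closing brackets left off both quotes). The third row is negative for both antibodies.

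The Part B SAP, section 5.4.1.1 item 5, uses the same rule: "PV: anti-DSG3 positive with anti-DSG1 negative or anti-DSG3 positive with anti-DSG1 positive".

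The programming note under Table 14.2.10.5.1 in the Part A shells reads: "Repeat Table 14.2.2.4.5 with the addition of page variable anti-dsg1 positive vs. anti-dsg1 positive anti-dag3 negative vs. neither positive". It also governs Tables 14.2.10.5.2 (mITT) and 14.2.10.5.3 (PP), which repeat that shell. The parent, Table 14.2.2.4.5, is the by-visit cumulative incidence of CDA without prednis(ol)one above 0.5 mg/kg, so its Week 5 row corresponds to the primary endpoint.

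**The concern.** A programming note is the operative instruction for a table. Here it disagrees with the SAP section it is meant to carry out, and nothing in the shells says which text prevails.

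The split has a purpose in this trial. Protocol section 6 accepts that some patients with clinical features of PF may be enrolled, and sections 1.2 and 1.4.2.1 say that the first 21 treated patients included both PV and PF. None of the other five splits in section 8.2.11 (age, gender, total antibody level, disease history, severity) separates the two. This is therefore the only planned Part A table set that shows whether the primary response holds in serologically defined PV. A first page built on anti-DSG1 does not show that.

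The output would give little warning. The notes for history type and severity each call for a defining footnote, and this one does not. The next set, Tables 14.2.10.6.1 to 14.2.10.6.3, is split by severity but carries the same Anti-DSG Profile title, both in the shells and in their table of contents.

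**Working it through.** No sample size or error rate is involved, and the plan gives no figure to reproduce. The check is whether each rule places every patient in exactly one group.

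**Inputs.** SAP section 6.1 plans for all four combinations of anti-DSG1 and anti-DSG3 status at baseline. Section 10 sets positivity at 14 or above for anti-DSG1 and 9 or above for anti-DSG3. The two rules come from section 8.2.11 and from the note; the note's dag3 is read as dsg3.

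**Rules.** Write D1 for anti-DSG1 positive and D3 for anti-DSG3 positive.

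- Section 8.2.11: PV = D3; PF = D1 and not D3; negative = not D1 and not D3.
- Note, read literally: page 1 = D1; page 2 = D1 and not D3; page 3 = not D1 and not D3.
- Note, read as separate groups: page 1 = D1 and D3; pages 2 and 3 unchanged.

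| Baseline profile | Count | Section 8.2.11 | Note, literal | Note, separate groups |
|---|---|---|---|---|
| DSG1+, DSG3+ | a | PV | page 1 | page 1 |
| DSG1+, DSG3− | b | PF | pages 1 and 2 | page 2 |
| DSG1−, DSG3+ | c | PV | no page | no page |
| DSG1−, DSG3− | d | negative | page 3 | page 3 |

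**Group sizes.** Let N = a + b + c + d.

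- Section 8.2.11: (a + c) + b + d = N.
- Note, literal: (a + b) + b + d = N + b − c.
- Note, separate groups: a + b + d = N − c.

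The SAP rule is exhaustive and mutually exclusive. The note is not exhaustive on either reading, because the c patients are always lost. On the literal reading it is also not mutually exclusive, because the b patients count twice. In that case, if b happened to equal c, the page totals would still add up to N and hide the error.

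**Effect on the first page.** The PV rate under section 8.2.11 has denominator a + c. The first page under the note has denominator a + b (literal) or a (separate groups). Neither is the PV group.

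**After the fix.** With the first level changed to D3, the four profiles fall in PV, PF, PV and negative, each once.

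**The case against.** The strongest reply is that this is a slip of one character. The plan's choice is correct and explicit in section 8.2.11 and is repeated in Table 14.1.2.1. The affected tables carry the same profile name in their title. The note has a second visible typo in the same line, and its second and third levels match the baseline shell, so the intended first level is plain. The shell log dates its version 2.0 to 20 December 2018, while the Part B SAP dates the final Part A SAP to 6 January 2019, so the correct text also appears to be the later one. Nothing in the documents shows that the tables were run as the note says.

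Most of this stands. The cause is probably clerical, and the analysis the plan intends is sound. But the instruction is wrong as written, and following it gives a wrong table.

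Two further replies limit the consequence. The split is one of six descriptive ones in an open-label pilot sized at 25 patients per part, and no decision rule depends on it. Patient-level antibody values (Listing 16.2.7.3) and disease status (Listing 16.2.4.1.5) are planned, so the correct split could be rebuilt. Both hold, and they keep the point small.

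A reader might also infer that PF-profile patients are certainly counted twice. The documents do not support that as a fact. A page variable normally takes one value per patient, and if the levels were meant to be separate the double count disappears. Only the omission of anti-DSG3-only patients holds on both readings.

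**Conclusion.** The note contradicts section 8.2.11, Table 14.1.2.1 and the Part B SAP, and should be corrected. Followed as written, patients with a PV profile who lack anti-DSG1 appear on no page of Tables 14.2.10.5.1 to 14.2.10.5.3; on the literal reading, PF-profile patients also appear on two.

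The size in patients cannot be derived, because the documents give no anti-DSG serostatus counts. Any head count would only multiply an assumed mix by the sample size. The failure to partition the population does not depend on the mix.

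Three larger conclusions might be drawn and are not supported:

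- That the primary result is affected. Tables 14.2.1.1 to 14.2.1.3 do not use the profile, so they are unchanged.
- That a group labelled PV is reported with the wrong patients. The parent table's columns are dose levels and a total, profile is a page variable, and the note labels no page PV.
- That this note is what prevents comparison with Part B. The parts differ in other ways that the correction leaves in place. Part A counts prednis(ol)one above 0.5 mg/kg at any time before the first CDA (section 8.1), while Part B looks at the day before (section 5.4.1). Part A groups by maximum dose, while Part B groups by the dose received before CDA. Part A uses the ITT, mITT and PP populations, while Part B's main efficacy population is mITT.

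**What to change.** Reword the note under Table 14.2.10.5.1 so that the page variable is: anti-dsg3 positive (PV, with or without anti-dsg1) vs. anti-dsg1 positive and anti-dsg3 negative (PF) vs. neither positive. This matches section 8.2.11 and Table 14.1.2.1 and removes the dag3 typo. The change carries over to Tables 14.2.10.5.2 and 14.2.10.5.3.

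The Part B SAP reports that the last Part A patient completed on 20 June 2019, so these tables may already exist. If so, confirm which rule was coded and reissue the three tables if it was the note's.

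As a minor editorial correction, retitle Tables 14.2.10.6.1 to 14.2.10.6.3 as by Pemphigus Severity, in the shells and in their table of contents.

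The cost is one programming note and one title, plus a rerun of three tables at most. No new data or analyses are needed.
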